7.9 Blinding

This is an open-label study and, therefore, no blinding is required.

7.10 Randomization and numbering of subjects

Because N01349 is an open-label, single-arm study, subjects will not be randomized to any treatment groups. The first 6 subjects meeting the eligibility criteria will be assigned to the Exploratory Cohort. Subsequent subjects will be assigned to the Confirmatory Cohorts.

An IRT system will be used to assign eligible subjects to a treatment regimen based on a predetermined packaging schedule provided by the Sponsor. The IRT will generate individual assignments for subject kits of BRV, as appropriate, according to the cohort assignment and dosing schedule.

After the ICF has been signed and dated, the subject will be enrolled in the study. The Investigator or designee will contact the IRT and provide brief details about the subject enrolled. Each subject will be assigned a 5-digit number that serves as the subject identifier throughout the study. The IRT will allocate kit numbers to the subject based on the subject number during the course of the study. The subject number will be required in all communications between the Investigator or designee and the IRT on a particular subject. Subject numbers and kit numbers will be tracked via the IRT.

8 STUDY PROCEDURES BY VISIT

A continuous consent process will be followed. Parent(s) or legal representative(s) will be informed about the study as early as possible and asked to sign the ICF after the occurrence of seizures has been confirmed by VEEG. During the course of the study, parent(s) or legal representative(s) will be updated about the care of their neonate, and continuous consent will be ensured by meetings between the Investigator (or designee) and the subject's parent(s) or legal

representative(s). Continuous consent will be documented in the subjects' medical charts and eCRF.

8.1 Exploratory Cohort

8.1.1 Screening Period

The Screening Period will be from the signing and dating of the written ICF by the parent(s) or legal representative(s) up to initiation of the first BRV dose. Any AEs, AEDs, concomitant medications, and medical procedures will be collected after the ICF is signed. The subject's eligibility to participate in this study will be assessed. The subject identification card will be dispensed.

The Screening Period starts up to 36 hours prior to the first administration of BRV. Phenobarbital, MDZ, PHT, LEV, or LDC may have been administered prior to the subject's enrollment into the study and/or at a location other than the study site.

Subjects will enter the Evaluation Period and start BRV treatment as soon as the occurrence of ENS per inclusion criterion 2a is confirmed by the Investigator based on local EEG. If preferred by the Investigator, the central VEEG reader can be consulted to confirm the required ENS.

The following assessments will be performed immediately before the first administration of BRV is initiated:

- Verification of inclusion/exclusion criteria. Confirmation on VEEG of ≥ 2 minutes of cumulative ENS or ≥ 3 identifiable ENS prior to entering the Evaluation Period (ENS is defined as a seizure lasting for at least 10 seconds on VEEG), despite treatment with 1 or more AEDs administered per SOC
- Vital signs (blood pressure, heart rate, respiratory rate [including apneas], oxygen saturation [pulse oximetry], and body temperature)
- Physical and neurological examination (Sarnat scale for subjects with HIE; physical examination will include a check for the presence of skin rash and skin hypersensitivity)
- Length
- Body weight
- Head circumference (to be taken within 7 days prior to drug administration, or at birth for subjects ≤ 7 days old)
- Heart rate monitoring
- Safety laboratory assessments (hematology, biochemistry, liver enzymes, and endocrinology)
- Thompson score (for subjects with HIE)
- Mechanical ventilation
- AEs as reported by the Investigator
- Recording of AEDs, concomitant medications, and medical procedures

Laboratory measurements will be performed by local laboratories unless historical data is available. Historical safety laboratory assessments, previously collected as standard of care, may

be accepted from referring hospitals as measurement prior to first use of BRV if performed 36 hours prior to the start of the Evaluation Period. In this case, test results will be considered medical history. Prior laboratory assessment results should be available and verified prior to initiation of the first BRV infusion.

At the determination of the Investigator, subjects achieving adequate seizure control following AED treatment per SOC will be considered AED responders. Those subjects will be classified as screen failures and will not be assigned to BRV treatment.

8.1.2 Evaluation Period

The first BRV infusion marks the starting point of the 48-hour Evaluation Period.

An initial iv dose of BRV (0.5mg/kg) will be administered as an approximately 15-minute infusion. At the discretion of the Investigator, 3 additional iv BRV doses can be administered, up to a total of 4 iv BRV doses (0.5mg/kg bid) during the 48-hour BRV Evaluation Period.

The following assessments will be performed after the end of the first BRV infusion:

- Vital signs (blood pressure, heart rate, respiratory rate [including apneas], oxygen saturation [pulse oximetry], and body temperature; at 0, 3, 6, 12, 24, and 48 hours)
- Physical and neurological examination (Sarnat scale for subjects with HIE; physical examination will include a check for the presence of skin rash and skin hypersensitivity; at 24 hours and 48 hours)
- Body weight (optional [at 24 and 48 hours]; dosage of BRV during the Evaluation Period will be based on the subject's weight measured prior to the start of the first BRV administration. However, dosage calculation can be adjusted to a more recent weight measurement, upon discretion of the Investigator, if weight is measured during the Evaluation Period)
- Confirmation of the primary cause of seizure (HIE, hemorrhage, or infarction; CNS malformations; CNS infections; undetermined causes [at 48 hours])
- N-PASS and EEG parameters for the assessment of sedation (at 48 hours)
- Video-EEG
- Heart rate monitoring (1, 2, 3, 6, 10, 12, 24, 27, 34, 36, and 48 hours)
- Three to 6 PK samples (30 to 60 minutes, 2 to 4 hours, and 8 to 12 hours after the start of the most recent BRV infusion; the same timepoints apply to the first and second day of the 48-hour Evaluation Period)
- Collection of AED PK sample 3 hours after the start of the initial BRV administration
- Safety laboratory assessments (hematology, biochemistry, liver enzymes, and endocrinology [at 48 hours])
 - Thompson score (for subjects with HIE [at 48 hours])
 - Mechanical ventilation
 - AEs as reported by the Investigator

- AEDs, concomitant medications, and medical procedures
- Infusion site reaction monitoring

8.1.3 BRV Extension Period

The BRV Extension Period is intended to bridge the time until subjects are old enough to participate in the long-term study. Subjects completing the Evaluation Period at a PNA of at least 28 days may directly roll over to the long-term study, if they meet the eligibility criteria. Those patients are not required to enter the BRV Extension Period.

At the end of the Evaluation Period, subjects who benefit from BRV treatment may enter the BRV Extension Period in accordance with the Investigator's opinion. Subjects participating in the BRV Extension Period will need to remain at the study site as long as BRV is administered iv or via the enteral route. Only subjects able to swallow oral BRV should be allowed to be treated at home during the BRV Extension Period. In this case the parent(s) or legal representative(s) will receive a dosing diary to record the home administration of oral BRV. If oral BRV administration is not possible, the subjects will be invited to return to the study site and receive iv BRV as indicated below. It will not be possible for subjects to receive iv BRV at any institutions other than the study site.

All subjects who participate in the BRV Extension Period must be offered entry into the long-term study, if they meet the eligibility criteria. Subjects will participate in the BRV Extension Period until they reach a stable condition that will allow them to enter the long-term study, if epilepsy is confirmed. The maximum anticipated duration of the BRV Extension Period per subject is up to 28 days of PNA (+7 days). For subjects entering the BRV Extension Period, study drug will be dispensed at the end of the Evaluation Period. Subjects not continuing the BRV treatment after they completed the Evaluation Period will not enter the BRV Extension Period but proceed immediately to the Safety Follow-Up Period (see Section 8.1.4).

For subjects treated at home with oral BRV during the BRV Extension Period, a total of 2 on-site visits may take place (Extension Period Visit 1 [EPV1], Extension Period Visit 2 [EPV2]). Extension Period Visit 1 will be performed at 7 ± 2 days after completion of the Evaluation Period (see Section 8.1.3.1). Extension Period Visit 2 will be performed on the same day when the subject enters the long-term study (see Section 8.1.3.2). If the long-term study is performed outside the N01349 hospital, an interval of up to 3 days between the N01349 EPV2 and follow-up study Entry Visit is allowed. In addition, an Unscheduled Visit or Telephone Contact can be performed, as needed. For subjects treated during the BRV Extension Period at the study site with iv BRV, assessments will be performed at timepoints described for EPV1 and EPV2.

During the BRV Extension Period, subjects may continue receiving iv BRV but must switch to BRV oral solution before entering the long-term study. The timepoint of the switch from iv to oral solution will be at the discretion of the Investigator. Subjects who are not able to be dosed with BRV oral solution when they reach 28 days of postnatal age may continue in the BRV Extension Period for an additional 7 days; subjects who are not able to be switched to BRV oral solution by the end of the additional 7 days of the BRV Extension Period will not be eligible for enrollment in the long-term study.

Subjects who participate in the BRV Extension Period will continue to receive the same BRV dosage administered at the end of the Evaluation Period (ie, BRV 0.5mg/kg bid). The BRV dose should not be increased, but may be decreased at the discretion of the Investigator.

8.1.3.1 Extension Period Visit 1

The EPV1 will be performed at 7 ± 2 days after completion of the Evaluation Period. The following assessments will be performed:

- BRV dispense
- AEs as reported by the Investigator
- AEDs, concomitant medications, and medical procedures
- Review of BRV dosing diary (only if oral BRV is administered at home)
- Infusion site reaction monitoring (for subjects treated with iv BRV)

For subjects unable to return to the hospital due to COVID-19, EPV1 can be performed remotely if BRV oral solution was dispensed at the time when the subject completed the Evaluation Period.

8.1.3.2 Extension Period Visit 2

The EPV2 should be performed on the same day when the subject enters the long-term study. The following assessments will be performed:

- Vital signs (blood pressure, heart rate, respiratory rate [including apneas], oxygen saturation [pulse oximetry], and body temperature)
- Physical and neurological examination (Sarnat scale for subjects with HIE; physical examination will include a check for the presence of skin rash and skin hypersensitivity)
- BRV administration/dispense. If the subject enters the long-term study, no study drug from N01349 will be dispensed at EPV2. If the subject does not enter the long-term study, BRV from N01349 will be administered for down-titration (only applicable to subjects from the Confirmatory Cohorts).
- BRV return
- Safety laboratory assessments (hematology, biochemistry, liver enzymes, and endocrinology)
- Bayley-III (for subjects continuing into the long-term study only and only for subjects enrolled in countries where a validated translation is available)
- AEs as reported by the Investigator
- AEDs, concomitant medications, and medical procedures
- Review of BRV dosing diary (only if oral BRV is administered at home)
- Infusion site reaction monitoring
- Confirmation/diagnosis of epilepsy
- Medical History (for subjects entering the long-term study)

8.1.3.3 Unscheduled Visit

An Unscheduled Visit can take place at any time during the BRV Extension Period. The following assessments will be performed:

- Vital signs (blood pressure, heart rate, respiratory rate [including apneas], oxygen saturation [pulse oximetry], and body temperature)
- Physical and neurological examination (Sarnat scale for subjects with HIE; physical examination will include a check for the presence of skin rash and skin hypersensitivity)
- AEs as reported by the Investigator
- AEDs, concomitant medications, and medical procedures
- Review of BRV dosing diary Infusion site reaction monitoring

8.1.3.4 Telephone Contact

For subjects receiving oral BRV at home, a Telephone Contact can be performed at any time during the BRV Extension Period. The following information will be collected by the Investigator:

- AEs
- AEDs, concomitant medications, and medical procedures
- Discussion of BRV dosing diary

8.1.4 Safety Follow-Up Period

Subjects will proceed to the Safety Follow-Up Period if they do not enter the BRV Extension Period. The visit will occur 30 ± 3 days after the final administration of BRV. The following assessments will be performed:

- Vital signs (blood pressure, heart rate, respiratory rate [including apneas], oxygen saturation [pulse oximetry], and body temperature)
- Physical and neurological examination (Sarnat scale for subjects with HIE; physical examination will include a check for the presence of skin rash and skin hypersensitivity)
- Body weight and length and head circumference
- Primary cause of seizure (HIE, hemorrhage, or infarction; CNS malformations; CNS infections; undetermined causes)
- N-PASS
- Safety laboratory assessments (hematology, biochemistry, liver enzymes, and endocrinology)
- AEs as reported by the Investigator
- AEDs, concomitant medications, and medical procedures
- Medical history (for subjects not entering the long-term study)

For subjects unable to return to the hospital due to COVID-19, the Safety Follow-Up Visit can be performed remotely. In this case vital signs, the physical and neurological examination, biometric and psychometric parameters, and the laboratory assessment may not be performed.

8.2 Confirmatory Cohorts

Based on the PK and safety data review of the Exploratory Cohort by the DMC, enrollment and BRV dosing for the Confirmatory Cohorts will begin. Three consecutive Confirmatory Cohorts (n=12 each) are planned. A PK and safety data review will be performed after completion of each of the 3 Confirmatory Cohorts. During the PK and safety data review, the recruitment of subjects will continue.

8.2.1 Screening Period

The Screening Period will be from the signing and dating of the written ICF by the parent(s) or legal representative(s) of the subject up to initiation of the first BRV dose. Any AEs, AEDs, concomitant medications, and medical procedures will be collected after the ICF is signed. The subject's eligibility to participate in this study will be assessed. The subject identification card will be dispensed.

The Screening Period starts up to 36 hours prior to the first administration of BRV. The treatment with one or more of the following AEDs prior to or at the time of enrollment: PB, MDZ, PHT, LEV ($\leq 60\text{mg/kg/day}$), or LDC (first-line, second-line, or subsequent treatment; choice of treatment, dose, and dosing regimen at the Investigator's discretion) may have started prior to the subject's enrollment in the study and/or at a location other than the study site.

At the determination of the Investigator, subjects achieving adequate seizure control following any of the following AEDs: PB, MDZ, PHT, LEV ($\leq 60\text{mg/kg/day}$), or LDC will be considered AED responders. Those subjects will be classified as screen failures and will not be assigned to BRV treatment.

8.2.1.1 Baseline Period

The Baseline Period will be up to 1 hour immediately prior to the start of initial BRV infusion and depend on seizure activity:

- For subjects with intermittent ENS: at least 1 hour prior to entering the Evaluation Period
- For subjects in status epilepticus: up to 30 minutes prior to entering the Evaluation Period. At least 15 minutes of continuous seizures, or 50% of cumulative seizure activity during a 30-minute interval are to be confirmed on EEG before the administration of BRV can start.

As soon as subjects are considered to be in status epilepticus, steps required for the preparation of the initial BRV infusion can be initiated (eg, assignment of BRV kits through interactive IRT and the dilution of BRV solution for iv infusion), even if the required EEG recording is not completed by that time.

The occurrence of ENS during the Baseline Period must be confirmed either by the local or central VEEG reader prior to drug administration. Preferably, the central VEEG reader should confirm the required ENS. Video-EEGs that are acquired per standard of care prior to consenting and meet study-specific technical and quality requirements (eg, ability for immediate cloud-based central review) can be used as part of the Baseline assessment VEEG.

The following assessments will be performed during the Baseline Period:

- Verification of inclusion/exclusion criteria. Confirmation on VEEG of ≥ 2 minutes of cumulative ENS or ≥ 3 identifiable ENS within the up to 1 hour prior to entering the Evaluation Period (ENS is defined as a seizure lasting for at least 10 seconds on VEEG), despite treatment with one or more AEDs per SOC
- Demographic data
- Medical history (including Apgar score)
- Vital signs (blood pressure, heart rate, respiratory rate [including apneas], oxygen saturation [pulse oximetry], and body temperature)
- Physical and neurological examination (Sarnat scale for subjects with HIE; physical examination will include a check for the presence of skin rash and skin hypersensitivity)
- Length
- Body weight
- Head circumference (Baseline measurement should be taken within 7 days prior to drug administration, or at birth for subjects ≤ 7 days old)
- Primary cause of seizure (HIE, hemorrhage, or infarction; CNS malformations; CNS infections; undetermined causes)
- N-PASS and EEG parameters for the assessment of sedation
- Video-EEG
- Heart rate monitoring
- Safety laboratory assessments (hematology, biochemistry, liver enzymes, and endocrinology)
- Thompson score (for subjects with HIE)
- Mechanical ventilation
- AEs as reported by the Investigator
- AEDs, concomitant medications, and medical procedures

Baseline laboratory measurements will be performed by local laboratories unless historical data is available. Historical safety laboratory assessments, previously collected as standard of care, may be accepted from referring hospitals as Baseline measurement if performed 36 hours prior to the start of the Evaluation Period. In this case, test results will be considered medical history. Prior laboratory assessment results should already be available at Baseline and verified prior to initiation of BRV administration.

8.2.2 Evaluation Period

The first administration of BRV marks the starting point of the Evaluation Period.

Up to 8 iv doses of BRV (1mg/kg bid) will be administered as an approximately 15-minute infusion during the 96-hour BRV Evaluation Period. The AED treatment initiated prior to first

administration of BRV can be continued if the subject is on a stable dose for at least 1 hour at the time the first BRV infusion is initiated.

If subjects do not benefit from BRV treatment after 96 hours of BRV administration, BRV administration will be stopped and replaced by another AED; however, the subjects' participation in the study will continue.

If subjects in the Confirmatory Cohort receive <8 BRV doses, those subjects are allowed to continue study participation and complete study assessments per [Table 5–2](#) with the exception of PK blood sampling. Those subjects should start the Down-Titration Period while completing the Evaluation Period in parallel for the full 96 hours.

After the enrollment of subjects, the weight of the subject will be measured and BRV will be given.

The following assessments will be performed after BRV administration:

- Vital signs (blood pressure, heart rate, respiratory rate [including apneas], oxygen saturation [pulse oximetry], and body temperature; at 0, 3, 6, 9, 12, 15, 18, 21, 24, 48, 72, and 96 hours)
- Physical and neurological examination (Sarnat scale for subjects with HIE; physical examination will include a check for the presence of skin rash and skin hypersensitivity [at 24, 48, 72, and 96 hours])
- Primary cause of seizure (HIE, hemorrhage, or infarction; CNS malformations; CNS infections; undetermined causes [at 96 hours])
- N-PASS and EEG parameters for the assessment of sedation (at 96 hours)
- Body weight (optional [at 24, 48, 72 and 96 hours]; dosage of BRV during the Evaluation Period will be based on the subject's weight measured prior to the start of the first BRV administration. However, dosage calculation can be adjusted to a more recent weight measurement, upon discretion of the Investigator, if weight is measured during the Evaluation Period)
- Video-EEG
- Heart rate monitoring
- Up to 6 PK samples (30 to 60 minutes, 2 to 4 hours, and 8 to 12 hours after the start of the most recent BRV infusion; the same timepoints apply to the first day and 1 of the 3 following days of the 96-hour Evaluation Period).
- Collection of AED PK sample 3 hours after the start of the initial BRV administration
- Safety laboratory assessments (hematology, biochemistry, liver enzymes, and endocrinology [at 24 and 96 hours])
- Thompson score (for subjects with HIE [at 96 hours])
- Mechanical ventilation

- Bayley-III (for subjects continuing into the long-term study only and only for subjects enrolled in countries where a validated translation is available)
- AEs as reported by the Investigator
- AEDs, concomitant medications, and medical procedures
- Infusion site reaction monitoring

8.2.3 BRV Extension Period

The BRV Extension Period is intended to bridge the period until subjects are old enough to participate in the long-term study. Subjects completing the Evaluation Period at a PNA of at least 28 days may directly roll over to the long-term study, if they meet the eligibility criteria. Those patients are not required to enter the BRV Extension Period.

At the end of the Evaluation Period, subjects who benefit from BRV treatment may enter the BRV Extension Period in accordance with the Investigator's opinion. Subjects participating in the BRV Extension Period will need to remain at the study site as long as BRV is administered iv. Only subjects able to swallow oral BRV should be allowed to be treated at home during the BRV Extension Period. If oral BRV administration is not possible, the subjects will be invited to return to the study site and receive iv BRV as indicated below. It will not be possible for subjects to receive iv BRV at any institutions other than the study site. All subjects who participate in the BRV Extension Period must be offered entry into the long-term study, if they meet the eligibility criteria. Subjects will participate in the BRV Extension Period until they reach a stable condition that will allow them to enter the long-term study, if epilepsy is confirmed. The maximum anticipated duration of the BRV Extension Period per subject is up to 90 days of PNA. For subjects entering the BRV Extension Period, study drug will be dispensed at the end of the Evaluation Period. Subjects not continuing the BRV treatment after they completed the Evaluation Period will not enter the BRV Extension Period but proceed immediately to the Down-Titration Period (see Section 8.2.4).

For subjects treated at home with oral BRV during the BRV Extension Period, a total of 2 on-site visits may take place (EPV1 and EPV2). Extension Period Visit 1 will be performed at 7 ± 2 days after completion of the Evaluation Period (see Section 8.2.3.1). Extension Period Visit 2 will be performed on the same day when the subject enters the long-term study (see Section 8.2.3.2). If the long-term study is performed outside the N01349 hospital, an interval of up to 3 days between the N01349 EPV2 and long-term study Entry Visit is allowed. In addition, an Unscheduled Visit or Telephone Contact can be performed, as needed. For subjects treated during the BRV Extension Period at the study site with iv BRV, assessments will be performed at timepoints described for EPV1 and EPV2.

During the BRV Extension Period, subjects may continue receiving iv BRV but must switch to BRV oral solution before entering the long-term study. The timepoint of the switch from iv to oral solution will be at the discretion of the Investigator.

Subjects who participate in the BRV Extension Period will continue to receive the same BRV dosage administered at the end of the Evaluation Period (ie, BRV 1mg/kg bid). The BRV dose should not be increased, but may be decreased at the discretion of the Investigator.

In the event that a long-term study is temporarily not available after the planned duration of the BRV Extension Period (28 [+7] days of PNA), subjects are allowed to remain in the BRV Extension Period until they reach a PNA of up to 90 days. For those subjects, the assessments planned for Unscheduled Visits (Section 8.2.3.3) will be conducted in intervals of approximately 30 days during the prolonged Extension Period.

8.2.3.1 Extension Period Visit 1

This visit will be performed at 7 ± 2 days after completion of the Evaluation Period. The following assessments will be performed:

- BRV dispense
- AEs as reported by the Investigator
- AEDs, concomitant medications, and medical procedures
- Review of BRV dosing diary (only if oral BRV is administered at home)
- Infusion site reaction monitoring (for subjects treated with iv BRV)

For subjects unable to return to the hospital due to COVID-19, EPV1 can be performed remotely if BRV oral solution was dispensed at the time when the subject completed the Evaluation Period.

8.2.3.2 Extension Period Visit 2

This visit should be performed on the same day when the subject enters the long-term study. The following assessments will be performed:

- Vital signs (blood pressure, heart rate, respiratory rate [including apneas], oxygen saturation [pulse oximetry], and body temperature)
- Physical and neurological examination (Sarnat scale for subjects with HIE; physical examination will include a check for the presence of skin rash and skin hypersensitivity)
- BRV administration/dispense. If the subject enters the long-term study, no study drug from N01349 will be dispensed at EPV2. If the subject does not enter the long-term study, BRV from N01349 will be administered for down-titration (only applicable to subjects from the Confirmatory Cohorts).
- BRV return
- Safety laboratory assessments (hematology, biochemistry, liver enzymes, and endocrinology)
- Bayley-III (for subjects continuing into the long-term study only and only for subjects enrolled in countries where a validated translation is available)
- AEs as reported by the Investigator
- AEDs, concomitant medications, and medical procedures
- Review of BRV dosing diary (only if oral BRV is administered at home)
- Infusion site reaction monitoring (for subjects treated with iv BRV)
- Confirmation/diagnosis of epilepsy

- Medical History (for subjects entering the long-term study)

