^d Subjects will attend EPV2 when they enter the long-term study. Before entering the long-term study, subjects must have been switched to BRV oral solution and be able to tolerate it. Subjects who have not been switched to BRV oral solution will not be permitted to continue into the long-term study. The timing of switching from iv to oral solution will be at the discretion of the Investigator. Subjects will continue to receive the same BRV dose administered at the end of the Evaluation Period.

^e Parent(s) or legal representative(s) will be informed about the study as early as possible and asked to sign the informed consent after the occurrence of seizures is confirmed on VEEG. Continuous consent will be ensured by meetings between the Investigator (or designee) and the subject's parent(s) or legal representative(s), during the conduct of the study.

^f To be performed on the first day of the Down-Titration Period only.

^g If the subject enters the long-term study, no study drug from N01349 will be dispensed in EPV2. If the subject does not enter the long-term study, BRV from N01349 will be administered for down-titration (only applicable to subjects from the Confirmatory Cohorts).

^h The Down-Titration steps and duration may be adjusted at the Investigator's discretion.

ⁱ Video-EEG will only apply to subjects of the Confirmatory Cohorts who complete the study after the Evaluation Period. The VEEG will be recorded for at least 1 hour on the final day of the Down-Titration Period. Additional VEEGs can be performed at any time during the Down-Titration Period at the Investigator's discretion.

^j Bayley-III assessment will be assessed for subjects continuing into the long-term study, in countries where a validated translation is available.

^k The recording of AEDs will include AEDs (BZDs and opiates) taken by the mother at the time of delivery. In addition, details regarding COVID-19 vaccination will be recorded as concomitant medication if mother was pregnant or breastfeeding when vaccinated.

^l Infusion site reactions will only be monitored for subjects receiving iv BRV. Monitoring for BRV infusion site reactions should take place during and 30 minutes after the end of the infusion.

^m Updated Medical History should be recorded at EPV2 for subjects entering the long-term study.

ⁿ Updated Medical History should be recorded for subjects not entering the long-term study.

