7 STUDY TREATMENTS

7.1 Description of investigational medicinal products

Only the following study drug will be supplied by UCB for N01349:

- BRV 10mg/mL iv solution in a 5mL vial.

For subjects who are switched to BRV oral solution in the BRV Extension Period, the following will be supplied by UCB:

- BRV oral solution, at concentrations of 10mg/mL, will be supplied in 300mL glass bottles.

Refer to the IMP Handling Manual for further details on the handling of BRV.

There is no placebo or reference product.

After the completion of the study, BRV treatment per SOC may be continued as prescribed but will not be provided by the Sponsor.

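### The EPV2 return and no-dispensing rules make no exception for the permitted wait of up to 3 days before off-site long-term study entry, so BRV could lapse for up to 5 doses (6 if none is given at EPV2)

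*Protocol*

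**What the plan says.** **Timing.** Protocol 8.2.3 and 8.2.3.2 place EPV2 on the day of long-term study entry. Section 8.2.3 adds one exception, for a long-term study run at a different hospital: "an interval of up to 3 days between the N01349 EPV2 and long-term study Entry Visit is allowed".

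**Supply at EPV2.** Section 8.2.3.2 states: "If the subject enters the long-term study, no study drug from N01349 will be dispensed at EPV2". Table 5-3 footnote g repeats the rule: "If the subject enters the long-term study, no study drug from N01349 will be dispensed in EPV2". BRV return is on the EPV2 procedure list in 8.2.3.2 and is marked for EPV2 in Table 5-3. Neither place makes an exception for the off-site interval.

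**Intent.** Section 8.2.3 says that babies in the Extension Period "will continue to receive the same BRV dosage administered at the end of the Evaluation Period", and Table 5-3 footnote d says the same: "Subjects will continue to receive the same BRV dose administered at the end of the Evaluation Period". Sections 1 and 5.1 require babies to be on oral BRV before they enter the long-term study.

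**Other supply text.** Section 7.1 says of the time after study completion that "BRV treatment per SOC may be continued as prescribed but will not be provided by the Sponsor". Section 7.7 requires unused drug to be either accounted for or returned, tells parents of babies treated at home to return what is left without naming a visit, and requires accountability to be done with parents and site staff present.

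**Taper.** Section 8.2.4 recommends down-titration of up to 1 week for babies who stop BRV or do not go on to the long-term study. Babies who roll over are not included.

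**The concern.** The visit rule and the supply rules fit together only when EPV2 and entry fall on the same day. Once an interval is permitted, a site that takes the bottle back and dispenses nothing sends the baby home without study drug until the Entry Visit. This looks like an oversight and not an intended stop, because 8.2.3 and footnote d both say the same dose continues.

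These are babies judged to benefit from BRV, who stay in the Extension Period "until they reach a stable condition that will allow them to enter the long-term study, if epilepsy is confirmed". A baby who stops BRV on purpose is recommended a taper, whereas a baby who lapses during an off-site transfer would have none. Withdrawal and rebound are a listed safety variable (Protocol 4.3.2 and 11.3.8), so an abrupt interruption is something the protocol itself treats as worth watching. A Telephone Contact or Unscheduled Visit in the interval is possible but not required.

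**Working it through.** **Inputs**
- Maximum interval: 3 days, taken as 72 h (Protocol 8.2.3).
- Dose: 1 mg/kg twice daily (Protocol 8.2.3).
- Dosing interval: 12 h (SAP 10.1).
- Half-life: about 9 h (Protocol 2.2, from the adult background). No neonatal value is given, so 18 h is used as an assumed alternative.
- Oral solution: 10 mg/mL in 300 mL bottles (Protocol 7.1).
- Minimum weight at enrollment: 2.3 kg (Protocol 6.1). An upper weight of 6 kg is assumed.

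**Check on the schedule.** Doses every 12 h over the 96-hour Evaluation Period give 96/12 = 8, which matches the up to 8 doses in Protocol 8.2.2. The protocol states no missed-dose figure of its own.

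**Missed doses.** Put EPV2 at time 0 and the Entry Visit at time T, where the long-term study gives the next dose. Count the doses due after 0 and before T. If no dose is given at EPV2, the dose due at time 0 is also missed and the last dose may be up to 12 h earlier. The share of the post-dose level remaining after t hours is 2^(−t/half-life), here with 9 h.

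| Interval | Dose at EPV2: missed | Hours since last dose | Level left | No dose at EPV2: missed | Hours since last dose | Level left |
|---|---|---|---|---|---|---|
| 24 h | 1 | 24 | 15.7% | 2 | 36 | 6.25% |
| 48 h | 3 | 48 | 2.48% | 4 | 60 | 0.98% |
| 72 h | 5 (at 12, 24, 36, 48, 60 h) | 72 | 0.39% | 6 | 84 | 0.155% |

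For comparison, an ordinary 12 h trough is 2^(−12/9) = 39.7%. With the assumed 18 h half-life, the three intervals leave 39.7%, 15.7% and 6.25% with a dose at EPV2, and 25.0%, 9.9% and 3.9% without, against 63.0% at 12 h. If 3 days is read as calendar days and stretches to about 80 h, the counts become 6 and 7.

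**Volume to bridge 3 days.** 1 mg/kg at 10 mg/mL is 0.1 mL/kg per dose. Six doses need 2.3 × 0.1 × 6 = 1.38 mL at 2.3 kg, or 6 × 0.1 × 6 = 3.6 mL at 6 kg. A 6 kg baby uses 6 × 0.1 × 2 = 1.2 mL per day, or 108 mL over 90 days, which is 36% of one bottle. The drug already dispensed would therefore normally cover the interval, although in-use shelf life is not given.

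**Where an event in the gap would be reported.** SAP 10.4.11 summarizes withdrawal and rebound by adverse events with onset in the Down-Titration Period. These babies have no such period, so the event misses that table. SAP 10.2 defines a treatment-emergent event as any with onset on or after first BRV, with no closing window, and SAP 10.2.1 tabulates these for the entire study. Protocol 11.1.2.3 collects serious events up to 30 days after each subject's end of study.

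**The case against.** The strongest reply is that no rule requires the baby to go without. Section 8.2.3.2 bars new dispensing but not use of drug dispensed earlier, and the volumes above show that an earlier bottle would usually last. BRV administration stays on the EPV2 list. The entry for BRV return does not say that every remaining dose must be surrendered before entry elsewhere, and 7.7 accepts accounting as an alternative to return. Sections 1 and 5.1, with footnote d, point towards continuation. The IMP Handling Manual and the long-term protocols are not available here and may supply drug. All of this stands, and it makes the gap conditional.

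It does not remove the problem. No text authorizes the family to keep the bottle past EPV2. The return entry and the advice in 7.7 both point to handing it back, and a site that follows them would be complying with the protocol. Prescribed BRV under 7.1 is optional and not sponsor-supplied.

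On reporting, a reader might infer that events in the gap would be lost to the safety analysis. The documents do not support that. Such an event misses one table but, once recorded, is a treatment-emergent event for the entire study. Serious events stay reportable, and Protocol 11.1.2.4 requires immediate reporting of new or worsening status epilepticus after BRV.

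The missing taper should not be pressed too far either. It is only recommended, and its steps and length are at the Investigator's discretion.

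**Conclusion.** The concern holds in conditional form. For off-site roll-overs, 8.2.3 permits a wait for which 8.2.3.2 and Table 5-3 footnote g make no provision. If the bottle is returned at EPV2 and no other document supplies drug, up to 5 twice-daily doses could be missed, or 6 if none is given at EPV2, without a taper. This takes 3 days as 72 h and assumes the next dose is given at the Entry Visit. Same-day entry, which is the default, leaves no gap.

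The number of babies affected is unknown and could be zero. Harm is plausible but not quantified: the residual-level figures rest on an adult or an assumed half-life and are tied to no clinical threshold. A reader might infer that the protocol orders an abrupt stop for every baby who rolls over. It does not: the exception is narrow, and the text as a whole intends treatment to continue.

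Sections 8.1.3 and 8.1.3.2 carry the same wording for the Exploratory Cohort. The DMC has already set the Confirmatory dose from that cohort, so the point matters there only if it is reopened.

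**What to change.** Add to 8.2.3.2 and to Table 5-3 footnote g:

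> If the Entry Visit is not on the same day as EPV2, drug accountability is done at EPV2 with the parents present, and the subject keeps (or, if needed, is dispensed) enough N01349 BRV oral solution to continue the same dose until the Entry Visit; the remaining bottle is returned afterwards.

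Keeping accountability at EPV2 meets the requirement in 7.7 that parents and site staff be present, so 7.7 needs no change and the family is not called back for it. A Telephone Contact at entry, to record adverse events and the last N01349 dose, would be useful but can remain optional. If the IMP Handling Manual or a long-term protocol already provides bridging drug, a cross-reference is still needed, because 8.2.3.2 as written bars dispensing of N01349 drug.

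The cost is one sentence in two places and a later bottle return for each off-site roll-over. Extra drug is normally nil. With the change, the number of missed doses falls to 0.
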